9.4.5 SAFETY ANALYSES

Safety Assessments

The safety of Olaparib, SBRT and pembrolizumab will be assessed by evaluating study drug exposure, adverse events, serious adverse events, oncology-related events, all deaths, as well as changes in laboratory determinations and vital sign parameters.

Duration of Study Drug

A summarization of the number of days and/or cycles subjects were exposed to study drug will be provided.

Adverse Events

Analyses of adverse events (and serious adverse events) will include only "treatment-emergent" events, i.e., those that have an onset on or after the day of the first dose of study drug. Analyses will not include those that have an onset greater than 30 days after the last dose of study drug. Treatment emergent adverse events will be summarized by system organ class and preferred term according to the MedDRA adverse event coding dictionary. The percentage of subjects experiencing an adverse event at a given severity, NCI CTCAE toxicity grade, and relationship to study drug will be provided.

Deaths

The number of subject deaths will be summarized (1) for deaths occurring while the subject was still receiving study drug in this study, (2) for deaths occurring off treatment within 30 days after the last dose of study drug, and (3) for all deaths in this study regardless of the number of days after the last dose of study drug. The relatedness of the deaths to the study drugs will also be provided.

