8.3 ADVERSE EVENTS AND SERIOUS ADVERSE EVENTS

8.3.1 DEFINITION OF ADVERSE EVENTS (AE)

Adverse event means any untoward medical occurrence associated with the use of an intervention in humans, whether or not considered intervention-related (21 CFR 312.32 (a)).

An adverse event can therefore be any unfavorable and unintended sign (including an abnormal laboratory finding, for example), symptom, or disease temporally associated with the use of a medicinal product or protocol-specified procedure, whether or not considered related to the medicinal product or protocol-specified procedure. Any worsening (i.e., any clinically significant

adverse change in frequency and/or intensity) of a preexisting condition that is temporally associated with the use of the Merck's product, is also an adverse event.

Merck product includes any pharmaceutical product, biological product, device, diagnostic agent or protocol-specified procedure, whether investigational (including placebo or active comparator medication) or marketed, manufactured by, licensed by, provided by or distributed by Merck for human use.

Adverse events may occur during the course of the use of Merck product in clinical trials, or as prescribed in clinical practice, from overdose (whether accidental or intentional), from abuse and from withdrawal.

Any medical condition that is present at the time that the participant is screened will be considered as baseline and not reported as an AE.

Changes in the severity of an AE will be documented to allow an assessment of the duration of the event at each level of severity to be performed. AEs, including lab work, characterized as intermittent require documentation of onset and duration of each episode.

All AEs, SAEs and other reportable safety events that occur after the consent form is signed but before treatment must be reported by the investigator if the participant is receiving placebo run-in or other run-in treatment, if the event causes the participant to be excluded from the study, and/or is the result of a protocol-specified intervention, including but not limited to washout or discontinuation of usual therapy, diet, or a procedure.

- All AEs from the time of treatment through 30 days following cessation of study treatment must be collected by the delegated study team. AEs that have an onset greater than 30 days after the last dose of study drug will not be collected.

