8.3.4 TIME PERIOD AND FREQUENCY FOR EVENT ASSESSMENT AND FOLLOW-UP

The occurrence of an AE or SAE may come to the attention of study personnel during study visits and interviews of a study participant presenting for medical care, or upon review by a study monitor. All AEs including local and systemic reactions not meeting the criteria for SAEs will be captured on the appropriate CRF. Information to be collected includes event description, time of onset, clinician's assessment of severity, relationship to study product (assessed only by those with the training and authority to make a diagnosis), and time of resolution/ stabilization of the event. All AEs occurring while on study must be documented appropriately regardless of relationship. All AEs will be followed to adequate resolution.

Any medical condition that is present at the time that the participant is screened will be considered as baseline and not reported as an AE. However, if the study participant's condition deteriorates at any time during the study, it will be recorded as an AE. UAPs will be recorded in the data collection system throughout the study.

Changes in the severity of an AE will be documented to allow an assessment of the duration of the event at each level of severity to be performed. AEs characterized as intermittent require documentation of onset and duration of each episode.

The PI will record all reportable events during the designated protocol specified timelines according to Section 8.4.1. SAEs will be followed until resolution or stabilization. At each study visit, the investigator will inquire about the occurrence of AE/SAEs since the last visit.

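### Section 9.4.5 defines treatment-emergent by onset date alone, so an adverse event that starts before the first dose and worsens on treatment may be left out of the safety tables

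*Combined protocol and SAP*

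**What the plan says.** Section 9.4.5 restricts the AE and serious AE analyses to treatment-emergent events, namely "those that have an onset on or after the day of the first dose of study drug". The upper limit is also set by onset: "Analyses will not include those that have an onset greater than 30 days after the last dose of study drug". Neither sentence mentions a change in grade.

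The recording rules in Section 8.3 do deal with worsening:

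- Section 8.3.1 says that clinically significant worsening "of a preexisting condition that is temporally associated with the use of the Merck's product, is also an adverse event".
- Section 8.3.4 sets the baseline: "Any medical condition that is present at the time that the participant is screened will be considered as baseline and not reported as an AE". It then adds that "if the study participant's condition deteriorates at any time during the study, it will be recorded as an AE".
- Both sections cover a grade change within an event: "Changes in the severity of an AE will be documented". The stated purpose is to measure how long the event lasts at each severity. A separate onset for each episode is required only for intermittent AEs.
- Section 8.3.1 requires an event between consent and treatment to be reported in listed circumstances. One of these is that it results from a protocol-specified intervention or procedure.

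**The concern.** The analysis rule and the recording rules do not match. Section 8.3 recognises two ways an AE can arise on treatment, as something new or as a worsening. Section 9.4.5 selects events on onset date only, so whether a worsening reaches the tables depends on the date in the onset field. The documents give no rule for that date.

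The safety and tolerability of radiotherapy added to olaparib is a secondary objective, and treatment-emergent AEs and serious AEs are its endpoint. With so few patients, one record moves a reported percentage visibly. If sites date worsening differently, the tables would partly reflect data-entry practice.

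**Working it through.** The plan states no figure to reproduce here, and it gives no rate of pre-dose events or of worsening. The check is to take each kind of event through the recording rules in 8.3.1 and 8.3.4 and then through the selection rule in 9.4.5.

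1. **New event after the first dose.** The onset is on treatment, so it is included.
2. **Condition present at screening that deteriorates on treatment.** The condition is baseline and has no AE record. The deterioration is the AE. If it is dated when it happens, its onset is on treatment and it is included. Section 8.3.4 collects a time of onset but does not say that this is the date of worsening.
3. **Intermittent AE first recorded before the first dose.** Each episode has its own onset. An on-treatment episode is included.
4. **Continuous AE first recorded before the first dose that rises in grade on treatment.** The severity change is documented, but nothing says that it opens a new record or a new onset date. If it stays one record, the onset is pre-dose and 9.4.5 excludes the event at every grade, including the grade reached on treatment.

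Cases 3 and 4 can describe the same amount of harm and yet be tabulated differently, only because one event paused and the other did not.

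**Can case 4 occur?** Yes, but the route is narrow. Screening runs from day -28 to day -1, and the baseline biopsy is taken within 14 days of starting therapy unless suitable archived tissue is used (Section 1.3 and its footnotes). Of the pre-treatment reporting triggers in 8.3.1, run-in treatment does not exist in this trial, and an event that causes exclusion belongs to a patient who is never treated. That leaves mainly events caused by a protocol procedure. Section 8.3.4 also asks for all AEs on study to be documented regardless of relationship, which could widen the group somewhat. The event must still be present at the first dose and then worsen.

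**Size per patient.** The planned number is 26 (Section 9.2). One patient missing from a tabulated category lowers its percentage by 1/26 = 0.038, or 3.8 percentage points. The documents do not allow the number of such patients to be estimated, and zero is possible.

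**Outputs not affected.** The safety lead-in uses its own DLT definition and window, from the first dose of radiation and olaparib to Cycle 2 Day 21 (Section 6.1.1). Deaths are summarised in 9.4.5 by timing relative to the last dose, and once for all deaths whatever the timing.

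**The case against.** The strongest reply is that Section 8.3 already does the work. A condition present at screening has no AE record, so there is no earlier onset to carry forward. The AE is the deterioration, and the ordinary reading dates it on treatment and counts it. Documenting the duration at each severity level also means that the timing of a grade change is captured. Laboratory and vital-sign changes are analysed separately, the safety summaries are descriptive, and no study decision rests on them.

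Most of this stands. It answers case 2, apart from the missing dating rule. It does not answer case 4, where an AE record with a pre-dose onset already exists. Capturing the date of a grade change does not help if the analysis selects on onset. Laboratory summaries cannot replace AE tables for symptoms such as pain.

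A reader might go further and infer that any pre-existing condition that worsens on treatment is dropped, so that toxicity is understated. The entry limits could seem to support this: hemoglobin from 9.0 g/dL, platelets from 100,000/µL, AST/ALT up to 5 x ULN with liver metastases (Table 1), and Grade 2 neuropathy (Section 5.2). The documents do not support that reading. All of these are present at screening, so their deterioration is an AE in its own right under 8.3.4. The laboratory values are also covered by the laboratory summaries. Neuropathy is not among the risks listed in Section 2.5.1.

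**Conclusion.** The point holds in a narrow form. Section 9.4.5 states an exclusive rule based on onset alone, and it can exclude a continuous AE that begins before the first dose and rises in grade on treatment. For conditions present at screening, worsening is naturally counted, and the only gap is the unstated onset date.

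The exclusion rests on one assumption: that such an AE is kept as a single record with its pre-dose onset. The documents permit this but do not state it. A downward bias in the reported toxicity is therefore possible but not shown, and no overall percentage can be put on it. The affected group is probably small and may be empty. Severity is minor: this is a cheap improvement to the definition.

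**What to change.** In Section 9.4.5, define a treatment-emergent event as one with onset on or after the first dose of any trial treatment, or one present before that dose that increases in CTCAE grade on or after it. Count it at its worst on-treatment grade. State that the worsening is dated when the grade increases, and apply the same dating rule to deteriorations recorded under 8.3.1 and 8.3.4. Referring to any trial treatment makes clear that radiation counts as well as the drugs. The existing 30-day upper limit can stay.

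The cost is one or two sentences and a comparison of pre-dose and on-treatment grade in the AE program. Severity changes are already documented, so no new data item is needed for recorded AEs. The downside is that reported AE rates may be slightly less favourable. In return, the counts no longer depend on how a site dates onset.

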1 PROTOCOL SUMMARY

1.1 SYNOPSIS

Protocol Title: A Phase II study of induction SBRT and olaparib followed by combination pembrolizumab/olaparib in gastric and gastroesophageal junction (GEJ) cancers

Objectives:

Primary Objective:

- To assess the anti-tumor efficacy of combined therapy as determined by measurement of objective response rate (ORR)

Secondary Objectives:

- To assess the anti-tumor efficacy of combined therapy as determined by measurement of overall survival (OS), progression free survival (PFS), duration of response (DOR) and disease control rate (DCR) as a total cohort and HRD (Homologous Recombination Deficiency) versus HR (Homologous Recombination) proficient.
- To evaluate the safety and tolerability of radiotherapy added to olaparib.

Tertiary/ Exploratory Objective:

- To define the effect of HRD on combination SBRT (Stereotactic Beam Radiation Therapy), olaparib, and pembrolizumab on immunomodulation as measured by immune cell infiltration and activation in plasma/serum assays and tissue.

Endpoint:

Primary Endpoint:

- Objective Response Rate of unirradiated tumors (ORR per RECIST 1.1)

Secondary Endpoints:

- Overall Survival (OS) from the initiation of therapy to the date of death or to the date of last follow-up.
- Progression Free Survival (PFS) from the initiation of therapy to the date of progression or to the date of last follow-up.
- Duration of response (DoR) defined as the time from documentation of tumor response to disease progression.

- Disease control rate (DCR) defined as the sum of partial response (PR), complete response (CR) and stable disease (SD).
- Treatment-emergent adverse events (AEs), serious adverse events (SAEs) of combination SBRT and olaparib

Tertiary/ exploratory:

- Immune changes in tumor tissue and plasma at baseline compared to after combination SBRT/olaparaib and after Olaparib/pembrolizumab
- Assess response based on HRD status, PD-L1 expression, MMR (Mismatch Repair)/MSI (Microsatellite Instability), and TMB (Tumor Mutational Burden) in tumor
- Changes in cytokines, ctDNA in plasma/serum
- Abscopal effect based on irradiated disease site

Population:

Sample size

- *Maximum number of participants that can be enrolled is 32 (allow for screen failures)*
- *Minimum number of participants to be enrolled 26 (between two cohorts: 13 in the HR deficient cohort, 13 in the HR proficient cohort) (number of participants needed to answer scientific question/aims)*

Phase:

II

Participating Sites:

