8.1.4.3 POST-TREATMENT VISITS

Safety Follow-Up Visit

The mandatory Safety Follow-Up Visit should be conducted approximately 30 days after the last dose of study treatment or before the initiation of a new anti-cancer treatment, whichever comes first. If the post-trial visit occurs less than 30 days after the last dose of study treatment, a subsequent follow-up phone call should be made at 30 days post the last dose of study treatment to determine if any adverse events have occurred since the post-trial clinic visit. All AEs that occur prior to the Safety Follow-Up Visit should be recorded. Participants with an AE of Grade > 1 will be followed until the resolution of the AE to Grade 0-1 or until the beginning of a new anti-cancer therapy, whichever occurs first. SAEs that occur within 90 days of the end of treatment or before initiation of a new anti-cancer treatment will also be followed and recorded. Participants who are eligible for retreatment/crossover with pembrolizumab (as described in Appendix 7) may have up to two safety follow-up visits, one after the Initial Treatment Period and one after the Second Course Treatment.

Follow-Up Visits

Participants who discontinue study treatment for a reason other than disease progression will move into the Follow-Up Phase and should be assessed every 12 weeks (42 ± 7 days) by radiologic imaging to monitor disease status. Every effort should be made to collect information regarding disease status until the start of new anti-cancer therapy, disease progression, death, end of the study or if the participant begins retreatment with pembrolizumab as detailed in Appendix 7. Information regarding post-study anti-cancer treatment will be collected if new treatment is initiated.

Participants who are eligible to receive retreatment with pembrolizumab according to the criteria in Appendix 7 will move from the follow-up phase to the Second Course Phase when they experience disease progression.

Survival Follow up

Participants who experience confirmed disease progression or start a new anticancer therapy, will move into the Survival Follow-Up Phase and should be contacted by telephone every 12 weeks to assess for survival status until death, withdrawal of consent, or the end of the trial, whichever occurs first. Patients will be followed for 5 years for survival.

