8.3.2 DEFINITION OF SERIOUS ADVERSE EVENTS (SAE)

Serious adverse event or serious suspected adverse reaction. An AE or suspected adverse reaction is considered "serious" if, in the view of either the investigator or sponsor, it results in any of the following outcomes: death, a life-threatening adverse event, inpatient hospitalization or prolongation of existing hospitalization, a persistent or significant incapacity or substantial disruption of the ability to conduct normal life functions, or a congenital anomaly/ birth defect. Important medical events that may not result in death, be life-threatening, or require hospitalization

may be considered serious when, based upon appropriate medical judgment, they may jeopardize the patient or subject and may require medical or surgical intervention to prevent one of the outcomes listed in this definition. Examples of such medical events include allergic bronchospasm requiring intensive treatment in an emergency room or at home, blood dyscrasias or convulsions that do not result in inpatient hospitalization, or the development of drug dependency or drug abuse.

Note: In addition to the above criteria, adverse events meeting either of the below criteria, although not serious per ICH definition, are reportable to the Merck in the same timeframe as SAEs to meet certain local requirements. Therefore, these events are considered serious by Merck for collection purposes.

- Is a new cancer (that is not a condition of the study);
- Is associated with an overdose.

All AEs, meeting serious criteria from the time of study treatment through 90 days following cessation of study treatment, or 30 days following cessation of study treatment if the participant initiates new anticancer therapy, whichever is earlier must be collected by the delegated study staff.

Refer to Table in Section 8.4.3.1 for additional details regarding each of the above criteria.

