9.3 POPULATION FOR ANALYSES

All eligible patients who has received any level of the target treatment will be included in the analyses for all preliminary, secondary and safety analysis except for the duration of response analysis. The analysis for duration of response will only include the patients who has responded.

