AEs associated with pembrolizumab exposure, including coadministration with additional compounds may represent an immunologic etiology. These immune-related AEs (irAEs) may occur shortly after the first dose or several months after the last dose of pembrolizumab treatment and may affect more than one body system simultaneously. Therefore, early recognition and initiation of treatment is critical to reduce complications. Based on existing clinical study data, most irAEs were reversible and could be managed with interruptions of pembrolizumab, administration of corticosteroids and/or other supportive care.

For suspected irAEs, ensure adequate evaluation to confirm etiology or exclude other causes.

Additional procedures or tests such as bronchoscopy, endoscopy, skin biopsy may be included as part of the evaluation. Based on the severity of irAEs, withhold or permanently discontinue pembrolizumab and administer corticosteroids. Dose modification and toxicity management guidelines for irAEs associated with pembrolizumab are provided in Table 10.

Table 10: Dose modification and toxicity management guidelines for immune-related AEs associated with pembrolizumab

General instructions:				

 1. Corticosteroid taper should be initiated upon AE improving to Grade 1 or less and continue to taper over at least 4 weeks. 2. For situations where pembrolizumab has been withheld, pembrolizumab can be resumed after AE has been reduced to Grade 1 or 0 and corticosteroid has been tapered. Pembrolizumab should be permanently discontinued if AE does not resolve within 12 weeks of last dose or corticosteroids cannot be reduced to ≤ 10 mg prednisone or equivalent per day within 12 weeks. 3. For severe and life-threatening irAEs, IV corticosteroid should be initiated first followed by oral steroid. Other immunosuppressive treatment should be initiated if irAEs cannot be controlled by corticosteroids. 				
Immune-related AEs	Toxicity grade or conditions (CTCAEv5.0)	Action taken to pembrolizumab	irAE management with corticosteroid and/or other therapies	Monitor and follow-up

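### Non-fatal serious adverse events that start 31 to 90 days after treatment ends are collected but left out of the planned safety summaries

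*Combined protocol and SAP*

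**What the plan says.** Section 9.4.5 introduces the rule with "Analyses of adverse events (and serious adverse events) will include only" treatment-emergent events, and then adds "Analyses will not include those that have an onset greater than 30 days after the last dose of study drug". The parenthesis in the first sentence brings SAEs under the same limit as other events.

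The collection rules for SAEs are longer. Section 8.3.2 covers "All AEs, meeting serious criteria from the time of study treatment through 90 days following cessation of study treatment", with the qualifier "or 30 days following cessation of study treatment if the participant initiates new anticancer therapy, whichever is earlier". Section 8.1.4.3 follows and records "SAEs that occur within 90 days of the end of treatment or before initiation of a new anti-cancer treatment". Section 8.3.6 requires reporting of SAEs over the 90-day window, with the same shortening to 30 days, and Section 8.3.6.1 does so for adverse events of special interest (AESIs). Non-serious events are different: Section 8.3.1 stops collecting them at 30 days.

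On timing, Section 2.5.1 and Appendix 6 both say that immune-related events "may occur shortly after the first dose or several months after the last dose of pembrolizumab treatment".

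On the population, Section 9.3 says "All eligible patients who has received any level of the target treatment will be included in the analyses", and this sentence covers the safety analysis as well as efficacy.

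**The concern.** Late serious toxicity is one of the things that an early trial of a checkpoint inhibitor with a PARP inhibitor and radiotherapy needs to describe. Here the sites are asked to collect SAEs for up to three months, and the analysis section then tells the statistician to drop the last two months of them. This is a stated rule, not an unstated detail, so an analyst who follows the plan faithfully will produce tables that omit serious events held in the database.

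Section 9.4.5 is also uneven. It counts deaths at any time after the last dose, with their relatedness, but not a serious event at the same time point that the patient survived. It gives no reason for the difference.

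The word eligible in Section 9.3 works in the same direction. A patient who was treated and later found not to meet a criterion would leave the safety tables, although that patient was exposed to the regimen.

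**Working it through.** The plan states no figure on this point, so there is none to reproduce. The check compares the collection window with the analysis window for each type of event.

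| Event type | Collected until (days after treatment ends) | Analysed until | Gap |
|---|---|---|---|
| Non-serious AE | 30 (8.3.1) | 30 (9.4.5) | none |
| Non-fatal SAE | up to 90; 30 if new anticancer therapy starts (8.3.2, 8.3.6) | 30 (9.4.5) | up to 60 days |
| AESI | up to 90; same shortening (8.3.6.1) | 30 (9.4.5) | up to 60 days |
| Death | no limit | no limit (9.4.5) | none |

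**Size of the window.** Maximum share of the post-treatment SAE window that is excluded = (90 − 30) / 90 = 60/90 = 67%. This is a share of calendar days. It is a maximum because the window can be shorter:

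- A patient who starts new anticancer therapy within 30 days of stopping has no gap.
- For a patient who starts it between days 31 and 90, the gap is less than 60 days. On the wording of 8.1.4.3, collection ends when the new therapy starts. On a literal reading of 8.3.2, it falls back to 30 days.

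**What an AESI adds.** Section 8.3.6.1 lists two: an overdose without symptoms or laboratory abnormality, and potential drug-induced liver injury. The first arises at dosing. The second is to be reported as an SAE in any case. The gap is therefore essentially one of non-fatal SAEs, and a late immune-related event would reach the database mainly by being serious.

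**Illustration.** The documents give no rate of SAEs on days 31 to 90. Assume a per-patient probability p of at least one such event that is collected, over the 26 planned patients, independently. The expected number of patients is 26p, and the chance of at least one is 1 − (1 − p)^26.

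| Assumed p | Expected patients (26p) | Chance of at least one |
|---|---|---|
| 2% | 0.5 | 41% |
| 5% | 1.3 | 74% |
| 10% | 2.6 | 94% |
| 20% | 5.2 | 99.7% |

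**Population.** Each treated patient removed as ineligible is 1/26 = 3.8% of the planned number. The documents do not say how many such patients to expect.

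**The case against.** The best case for leaving the plan alone is that the safety analysis is descriptive, and no test or stopping rule depends on the 30-day cut. Late SAEs also still reach the data and safety monitoring committee, the ethics board and the drug supplier through the reporting rules, as do SAEs in a treated patient later found ineligible. This is correct, and it limits the consequence to the published safety summaries. It does not explain why events worth collecting should be left out of those summaries.

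A reader might infer several stronger points that the documents do not support:

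- **That all late events are discarded.** Deaths are summarised whenever they occur, so a late fatal event is lost only from the coded event tables. Late non-serious events are not discarded by the analysis, because they are never collected.
- **That two-thirds of post-treatment SAEs are lost.** That would need a constant hazard and a full 90 days of collection for every patient. The protocol itself shortens the window when new therapy starts.
- **That late immune events are expected.** The protocol says only that they may occur.
- **That late radiation toxicity is generally lost.** Section 2.5.1 does list late radiation effects, but radiotherapy is given in Cycle 1 and the 30-day clock starts at the last dose of study drug. For a patient who stays on treatment, months after radiotherapy fall inside the analysis window. The loss concerns only effects that appear after drug has stopped.
- **That the plan pools Cycle 1 with the pembrolizumab cycles.** Section 9.4.5 is silent on analysis by treatment period. The synopsis names the endpoint as events and "serious adverse events (SAEs) of combination SBRT and olaparib", but the endpoint lists in Sections 3 and 9.1 omit that qualifier, although the Section 3 objective keeps the focus on radiotherapy added to olaparib. A separate table would help, but its absence does not contradict a stated rule.

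**Conclusion.** The point holds in a limited form. Section 9.4.5, followed as written, excludes non-fatal SAEs (including potential drug-induced liver injury reported as an SAE) with onset on days 31 to 90, although Sections 8.1.4.3, 8.3.2 and 8.3.6 have them collected, recorded and reported. Together with the eligibility condition in Section 9.3, the stated rules can only lower the count of harm reported.

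The excluded period is at most 60 of 90 days. How many events this involves cannot be derived from the documents. Under the assumed rates of 2% to 20%, it would be about 0.5 to 5.2 patients of 26, and from 5% upwards at least one affected patient is more likely than not. The primary response analysis is untouched. The change should be made because the omission is systematic, concerns serious events, and costs almost nothing to remove.

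**What to change.** 1. In Section 9.4.5, summarise SAEs and AESIs over the full collection window of Section 8.3.2 (90 days, or 30 days if new anticancer therapy starts), and keep the 30-day limit for non-serious events only. State the window in the table titles. Align the wording of 8.1.4.3 with that of 8.3.2, so that the end of the window is the same when new therapy starts.
2. In Section 9.3, define the safety set as all patients who received any study treatment, whether or not they are later found eligible.
3. Optionally, because the synopsis frames the safety endpoint around SBRT with olaparib, add one table of events with onset before the first pembrolizumab dose. It would complement the overall tables, since on its own it would miss late radiation effects.

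The SAE and AESI data are already collected, and no visit or procedure changes. The cost is revised wording, slightly more analysis work and, if the option is taken, one more table. Reported toxicity may rise.
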